6.4.1 Immobilization and Simulation

Patients will be positioned supine in an Alpha Cradle or equivalent immobilization device will be custom made for each patient. Treatment planning CT scans will be required to define gross tumor volume (GTV). Multi-phasic IV contrast is recommended for the planning CT (arterial phase and/or delayed phase imaging recommended for GTV delineation, and venous phase for portal vein thrombosis delineation). If oral contrast is used at simulation, similar timing and volume of oral contrast is to be used at the time of treatment.

Breath-hold CT or average phase CT (from 4D-CT) may be used as the baseline CT for radiation therapy planning. All scans used for target delineation should be fused to each other so that the livers are registered to each other for target delineation. Registration will be performed with the best-fit liver-to-liver image registration, focusing on the region of the PTVs if deformation or rotation occurs between scans. Breathing motion management is recommended if breathing motion is >5 mm. Motion management can be addressed using respiratory gating, active breathing control (ABC), or abdominal compression.

6.4.2 Target volumes

Gross tumor volume (GTV) is defined as HCC focus that is visualized on contrast imaging, usually best seen on arterial phase (as hyperintensity) or washout out at portovenous/ delayed phase.

Clinical target volume (CTV) is defined as GTV with expansion to include the lipiodol stained area.

Planning target volume (PTV) will provide margin around each CTV to compensate for respiratory motions. Individualized margin will be added to CTV to form the planning target volume (PTV) to compensate for respiratory motions. The margin recipe depends on the motion management solution utilized. Typically, a minimum PTV of 4mm around each CTV is required and the maximum permitted PTV is 20mm.

6.4.3 Dose Specifications

Treatment Schedule: Treatment will be delivered in 5 fractions. The time between fractions should be between 24 and 72 hours, with treatment delivered to all targets over 5 to 15 days.

Prescription Dose: Absorbed dose: 27.5 Gy - 50 Gy in 5 fractions. The prescription dose may be 50 Gy, 45 Gy, 40 Gy, 35 Gy, 30 Gy or 27.5 Gy in 5 fractions, based on normal tissue constraints. The minimal planned prescription dose to PTVs is 27.5 Gy. The dose to multiple PTVs may be different. The goal is to use the highest allowable prescription dose to the primary target, while respecting normal tissue constraints. Dose prescription is based on the volume of normal tissues irradiated (correlated with mean liver dose), as well as proximity of stomach, duodenum, small and large bowel (GI luminal structures) to the target volumes, as normal tissue constraints must be maintained in this study.

Dose Specification: The prescription isodose should encompass 95% of PTV. If there are multiple PTVs, each should be planned for one of the prescription doses listed above, with each specific covering isodose planned to encompass 95% of each PTV, with normalization to the PTV receiving the highest dose. The highest allowable doses to the target volumes that maintain normal tissue constraints should be used. A goal is that 100% of the CTV is encompassed by the prescription dose.

Vascular tumor thrombosis (e.g., portal vein thrombosis) dose should be the same as the HCC prescription dose. However, lower doses are acceptable if required to maintain normal tissue limits, since the cancer density may be lower than parenchymal HCC.

Dose prescription based on mean liver dose (MLD)

| Prescription dose | Liver – GTV mean dose | |
|-------------------|-----------------------|-------------|
| | Ideal | Acceptable |
| 50Gy | ≤13Gy | 13-13.2Gy |
| 45Gy | ≤13Gy | 15-15.2Gy |
| 40Gy | ≤15Gy | 15-15.2Gy |
| 35Gy | ≤15.5Gy | 15.5-15.7Gy |
| 30Gy | ≤16Gy | 16-16.2Gy |
| 27.5Gy | ≤17Gy | 17-17.2Gy |

Organ-at-risk (OAR) dose constraints

Compliance Criteria:

| | Ideal | Acceptable |
|-------------------------------------------------------|-------|-----------------|
| Priority 1: Mandatory dose constraints | | |
| Stomach, small intestine, duodenum: Max (to 0.5cc) | 30Gy | >30Gy but ≤32Gy |
| Large bowel, oesophagus: Max (to 0.5cc) | 32Gy | >32Gy but ≤34Gy |
| Spinal cord + 5mm: Max (to 0.5cc) | 25Gy | >25Gy but ≤28Gy |
| Kidney: Bilateral mean dose | ≤10Gy | >10Gy but ≤12Gy |

| Priority 2: Non-mandatory dose constraints | |
|-------------------------------------------------------|-----------|
| Heart: Max (to 30cc) | <30Gy |
| Gall bladder: Max (to 0.5cc) | <55Gy |
| Common bile duct: Max (to 0.5cc) | <50Gy |
| Central biliary structure (main portal vein + 1.5cm): | V40 <21cc |
| Skin: Max (to 0.5cc) (external + 5mm) | <32Gy |
| Great vessel: Max (to 0.5cc) | <60Gy |

Total Treatment Duration

- Per protocol: All treatment falls within 15 calendar days
- Variation Acceptable: All treatments fall within 16 to 21 calendar days
- Deviation Unacceptable: All treatments that take 22 or more calendar days to complete

(a) PTV dosimetry

- The intent is for prescription dose to cover 95% of each PTV
- The PTV should be treated to as high a dose as possible, respecting normal tissue constraints (as above)
- Modifying required PTVs due to close proximity of adjacent OARs is not permitted

| | |
|-------------------------|-----------------------------------------------|
| Dose to 95% PTV | |
| Per Protocol | Prescription dose +/- 5% |
| Variation acceptable | 90% - 110% of prescribed dose |
| Derivation unacceptable | <90% or >110% of prescribed dose, or <25Gy |

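### The 45 Gy row of the mean-liver-dose table leaves doses above 13 and below 15 Gy unclassified, yet calls the higher 15-15.2 Gy Acceptable

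*Protocol*

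**What the plan says.** Section 6.4.3 of the protocol offers six prescription levels and ties the choice among them to normal tissue dose: "Dose prescription is based on the volume of normal tissues irradiated (correlated with mean liver dose), as well as proximity of stomach" and the other luminal gut structures. It asks for the highest dose that the normal tissue limits permit and says that those limits have to be kept.

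The table headed "Dose prescription based on mean liver dose (MLD)" gives two columns for the mean dose to liver minus GTV, Ideal and Acceptable. The row in question is "45Gy | ≤13Gy | 15-15.2Gy". Its neighbours are "50Gy | ≤13Gy | 13-13.2Gy" above and "40Gy | ≤15Gy | 15-15.2Gy" below. The three lowest levels read "35Gy | ≤15.5Gy | 15.5-15.7Gy", "30Gy | ≤16Gy | 16-16.2Gy" and "27.5Gy | ≤17Gy | 17-17.2Gy".

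The organ-at-risk tables that follow in the same section have no row for the liver, so this table holds the only liver dose limit in section 6.4.3.

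**The concern.** A limit on normal liver dose should get stricter or stay level as the dose rises. The 45 Gy row does the reverse: 14 Gy has no class and 15.1 Gy passes. The row joins the Ideal value of the 50 Gy row to the Acceptable value of the 40 Gy row, which suggests a slip in one cell.

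What is at stake is the prescribed dose. Because the protocol asks planners to go as high as the limits allow, the position of the ceiling decides whether some patients receive 45 or 40 Gy. If the ceiling is read too high, the liver receives more dose than was intended, in patients with tumours of 5-25 cm and Child-Pugh class A-B7. Section 6.4.4 lists radiation-induced liver disease as a risk, and grade 4 or 5 hepatic events count towards the stopping rule in section 8.3. If it is read too low, the tumour is underdosed.

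**Working it through.** **Inputs.** All limits come from the mean-liver-dose table in section 6.4.3.

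**Step 1: compare the rows.** Gap = lower Acceptable limit − Ideal limit. Width = upper Acceptable limit − lower Acceptable limit.

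| Prescription | Ideal (Gy) | Acceptable (Gy) | Gap (Gy) | Width (Gy) |
|---|---|---|---|---|
| 50 Gy | ≤13 | 13-13.2 | 13 − 13 = 0 | 0.2 |
| 45 Gy | ≤13 | 15-15.2 | 15 − 13 = **2** | 0.2 |
| 40 Gy | ≤15 | 15-15.2 | 15 − 15 = 0 | 0.2 |
| 35 Gy | ≤15.5 | 15.5-15.7 | 15.5 − 15.5 = 0 | 0.2 |
| 30 Gy | ≤16 | 16-16.2 | 16 − 16 = 0 | 0.2 |
| 27.5 Gy | ≤17 | 17-17.2 | 17 − 17 = 0 | 0.2 |

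Five rows follow one rule: Acceptable runs from the Ideal limit to that limit plus 0.2 Gy. The 45 Gy row does not. One visible result is that at a mean liver dose of 13.1 Gy a 50 Gy plan is Acceptable while a 45 Gy plan is in neither column.

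**Step 2: list the corrections that close the gap.**

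- A: Ideal ≤15, Acceptable 15-15.2. Width 15.2 − 15 = 0.2 Gy; ceiling 15.2 Gy.
- B: Ideal ≤13, Acceptable 13-13.2. Width 13.2 − 13 = 0.2 Gy; ceiling 13.2 Gy.
- C: Ideal ≤13, Acceptable 13-15.2. Width 15.2 − 13 = 2.2 Gy; ceiling 15.2 Gy.

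A and B fit the rule of the other rows. C closes the gap but breaks the 0.2 Gy pattern. The neighbouring rows do not decide between A and B: A makes the 45 Gy row equal to the 40 Gy row, and B makes it equal to the 50 Gy row.

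**Step 3: classify a 45 Gy plan under each reading.**

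| Mean liver dose (Gy) | As printed | A | B | C |
|---|---|---|---|---|
| above 13 to 13.2 | no class | Ideal | Acceptable | Acceptable |
| above 13.2, below 15 | no class | Ideal | above limit | Acceptable |
| 15 to 15.2 | Acceptable | Ideal at 15, Acceptable above | above limit | Acceptable |
| above 15.2 | above limit | above limit | above limit | above limit |

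**Step 4: size the consequence.** Up to 13.2 Gy the plan stays at 45 Gy under all three corrections. From above 13.2 to 15.2 Gy it stays at 45 Gy under A and C. Under B it must be replanned to 13.2 Gy or lower, or step down to 40 Gy: 45 − 40 = 5 Gy, and 5/45 = 11.1%.

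Within the unclassified range, the part where the prescription depends on the correction is (15 − 13.2)/(15 − 13) = 1.8/2 = 90%. This is a share of a dose interval, not of patients. The 15-15.2 Gy band does have a printed class and is in doubt only if B was meant.

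**Step 5: could plans land in the gap?** As an illustration only, assume that mean liver dose scales with the prescription. A 45 Gy plan at 13 to 15 Gy then corresponds to 13 × 50/45 = 14.4 to 15 × 50/45 = 16.7 Gy at 50 Gy. Those plans fail the 50 Gy row and would be tried next at 45 Gy. The protocol gives no distribution of liver doses, so the number of patients cannot be estimated.

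**The case against.** The strongest reply is that these are upper limits. If 15-15.2 Gy is Acceptable, no planner has a dosimetric reason to reject 14 Gy, so a sensible reading gives a working ceiling of 15.2 Gy with only the label unclear. The change of prescription then arises only if the printed Acceptable cell is the wrong one. This is fair as far as it goes, and it is why the 45-versus-40 Gy consequence is conditional. But it assumes the Acceptable cell is the correct one, which the document does not establish.

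Second, the table has no class for plans beyond Acceptable, and mean liver dose is not among the constraints labelled mandatory, so the step-down under B is an inference. The section does say that normal tissue limits have to be kept, which makes a hard limit the likelier intent, but the protocol does not spell it out.

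Third, only plans above 13.2 and up to 15.2 Gy depend on the answer, so a re-check could be confined to these. That is correct on the arithmetic. Starting from 13 Gy is slightly wider and does no harm, since plans between 13 and 13.2 Gy also lack a printed class.

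Fourth, correction A differs from the printed row by one digit, so a misread digit cannot be excluded from the text alone. The row is complete and aligned with its neighbours and nothing points to a misreading, but the source PDF should be looked at first.

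Finally, the effect is small: one level in a 33-patient trial in which proximity to the gut also drives the dose.

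**Conclusion.** The point holds. The 45 Gy row is wrong as printed: it leaves a 2 Gy range without a class, against 0 Gy in the other five rows, and passes a higher liver dose than the one it leaves out. The ceiling at 45 Gy is 15.2 Gy under A or C and 13.2 Gy under B, and nothing in the protocol settles which was meant.

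The consequence is bounded. It concerns one of six levels and one prescription step. No reading permits more than 15.2 Gy, which the 40 Gy row already accepts. The 5 Gy difference arises only if B is the intended row, if values beyond Acceptable are not allowed, and if the plan cannot be brought down to 13.2 Gy. The number of patients affected may be zero. There is no effect on the sample size or the primary analysis. It should still be fixed, because it is a treatment threshold that planners are told to work up to.

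**What to change.** The radiation oncology and physics leads state the intended 45 Gy limits and correct the row by amendment to one of:

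- Ideal ≤15 Gy, leaving Acceptable at 15-15.2 Gy;
- Acceptable 13-13.2 Gy, leaving Ideal at ≤13 Gy;
- Acceptable 13-15.2 Gy, if a wider band was intended.

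They then re-check any 45 Gy plans already made with a mean liver dose above 13 Gy, starting with those above 13.2 and up to 15.2 Gy. Until the amendment is in force, new 45 Gy plans above 13 Gy go to the same leads for a decision.

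Applying the stricter 13.2 Gy ceiling in the meantime is an option, not a requirement. It protects the liver, but it overrides a printed Acceptable value. Where replanning fails it also costs 5 Gy of tumour dose, against the instruction to treat as high as the limits allow.

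The cost is one table cell, a short period of referral and a re-check of any plans concerned. The sample size and the analysis do not change.

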6.4.4 Radiation Therapy Adverse Events

The criteria used for the grading of toxicities encountered in this study are Common Toxicity Criteria (CTC) version 4.0.

Very likely (80-90%)

- Fatigue
- Skin irritation, itchiness, discomfort
- Transient changes in blood work (decrease in blood counts, increase in liver enzymes), without symptoms

Less likely (<30%)

- Nausea, vomiting

- Gastric, esophagus, small bowel or large bowel irritation/ulceration, bleeding, fistula, obstruction or changes in motility following therapy (may require medications or surgery) (<10% permanent changes)
- Chest wall pain, rib fracture (<10%)

Less likely, but serious (<20%)

- Radiation-induced liver disease (RILD) (<5%). Classic RILD is a clinical diagnosis of anicteric ascites, hepatomegaly and elevation of alkaline phosphatase relative to other transaminases that may occur 2 weeks to 3 months following radiation to the liver.
- Non-classic RILD includes elevation of liver enzymes and/or any decline in liver function within 12 weeks from start of therapy (~20%). RILD can lead to liver failure that could lead to death.
- Permanent thrombocytopenia (<1%); this may lead to bleeding
- Kidney injury (<1%); this may lead to changes on imaging

6.4.5 Radiotherapy Toxicity Assessment During Therapy

Patients will be assessed at least once during radiation therapy for toxicity. Radiation therapy will continue as planned as long as there is no grade 3 or 4 toxicity, bilirubin ≤ 3.0 mg/dL, Child Pugh score ≤ 7 and the treating physician recommends continuation. Otherwise, a delay in radiation therapy should occur with possible continuation of radiation after toxicities resolve. If the patient discontinues radiation therapy prematurely, the patient may be considered for study Avelumab, if the Child score is Child Pugh ≤ 7 and the treating physician recommends protocol treatment continuation.

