6.4.6 Radiation Modification Table

| TOXICITY | MODIFICATION |
|--------------------------------------------------|---------------------------------------------------------------|
| Hematological | |
| Grade 1 or 2 | Continue radiation |
| Grade 3 | Hold radiation until \leq grade 2, then continue |
| Grade 4 | Hold radiation 1 week and until \leq grade 2, then continue |
| Gastrointestinal (nausea, vomiting and diarrhea) | |
| Grade 1 or 2 | Continue radiation |
| Grade 3 | Hold radiation until \leq grade 2, then continue |
| Grade 4 | Discontinue radiation |
| Hepatic dysfunction | |
| Grade 1 or 2 AST or ALT | Continue radiation |
| Grade 3 AST or ALT | Hold radiation until \leq grade 2, then continue |
| Grade 4 AST or ALT | Hold radiation 1 week and until \leq grade 2, then continue |
| Bilirubin ≤ 3.0 mg/dL | Continue radiation |
| Bilirubin > 3.0 mg/dL | Hold radiation until improved ≤ 3.0 , then continue |

| | |
|-------------------------|----------------------------------------------------|
| Child-Pugh score >7 | Hold radiation until improves to CP score ≤ 7 |
| Other non-hematological | |
| Grade 1 or 2 | Continue radiation |
| Grade 3 | Hold radiation until \leq grade 2, then continue |
| Grade 4 | Discontinue radiation |

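### For grade 4 gastrointestinal and other non-haematological toxicity during SBRT, Protocol 6.4.5 and 6.4.6 give different instructions, and the toxicity holds in 6.4.6 are not reconciled with the timing rules of 6.4.3

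*Protocol*

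**What the plan says.** Three subsections of the Protocol govern an SBRT course that runs into toxicity.

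- **6.4.5** sets the conditions for carrying on: no grade 3 or 4 toxicity, bilirubin no higher than 3.0 mg/dL, Child-Pugh score no higher than 7, and the treating physician's recommendation. If they are not met: "Otherwise, a delay in radiation therapy should occur with possible continuation of radiation after toxicities resolve". Grades 3 and 4 are treated alike, whatever the type of toxicity. The section goes on to say that a patient who stops radiation early may still be considered for avelumab, but it does not tie early stopping to any toxicity or grade.
- **6.4.6** separates types and grades. Grade 4 gastrointestinal and grade 4 other non-haematological toxicity carry the entry "Discontinue radiation". Grade 4 haematological and grade 4 AST or ALT events carry an entry that begins "Hold radiation 1 week and until" and then requires grade 2 or lower before continuing. Grade 3 events, bilirubin above 3.0 mg/dL and Child-Pugh above 7 are held until recovery. No maximum hold is given.
- **6.4.3** plans five fractions and fixes their timing: "The time between fractions should be between 24 and 72 hours, with treatment delivered to all targets over 5 to 15 days". It then scores total duration in three bands. A course of up to 15 calendar days counts as per protocol, one of 16 to 21 days as an acceptable variation, and the last band reads "Deviation Unacceptable: All treatments that take 22 or more calendar days to complete". None of the bands mentions toxicity holds.

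**The concern.** The first issue is a direct one. A patient with a grade 4 gastrointestinal or other non-haematological event is, under one subsection, delayed with resumption left open and, under the next, taken off radiation. There is no cross-reference or order of precedence. Whether such a patient receives the remaining fractions changes both the SBRT dose delivered and the exposure to further toxicity, and SBRT is one of the three components under test. The protocol itself treats these events as important: grade 4 gastrointestinal toxicity is among the events monitored under the early stopping rule in 8.3.

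The second issue is that the safety table and the schedule were not written to fit together. A site that follows 6.4.6 may depart from 6.4.3, and nothing says how that departure is to be recorded. Some holds are foreseeable: 3.1 admits patients up to Child-Pugh B7, so a one-point worsening in a patient who enters at 7 triggers the Child-Pugh hold. Section 6.5 also times avelumab from completion of SBRT, so a long hold moves the next component as well.

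**Working it through.** **Step 1. The instructions side by side.**

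| Event during SBRT | 6.4.5 | 6.4.6 | Compatible? |
|---|---|---|---|
| Grade 3, any type | delay, may resume | hold, resume at grade 2 or lower | yes |
| Grade 4 haematological; grade 4 AST or ALT | delay, may resume | hold at least 1 week, resume at grade 2 or lower | yes |
| Bilirubin above 3.0 mg/dL; Child-Pugh above 7 | delay, may resume | hold until recovered | yes |
| Grade 4 gastrointestinal | delay, may resume | stop | **no** |
| Grade 4 other non-haematological | delay, may resume | stop | **no** |

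The conflict is confined to the last two rows.

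**Step 2. The plan's own schedule.** Inputs from 6.4.3: 5 fractions, hence 4 gaps, each of 24 to 72 hours (1 to 3 days). Count the day of the first fraction as day 1:

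calendar days = 1 + sum of the 4 gaps

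- all gaps 24 h: 1 + 4 × 1 = 5 days
- all gaps 72 h: 1 + 4 × 3 = 13 days

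The result, 5 to 13 days, starts at the stated lower limit of 5 and lies inside the stated upper limit of 15.

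**Step 3. The one-week hold against the fraction interval.** One week is 7 × 24 = 168 h. This exceeds 72 h in every case.

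**Step 4. One held gap against total duration.** Let *h* be the gap in days between the fractions on either side of the hold, with the other three gaps at 1 to 3 days:

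- shortest course: 1 + 3 × 1 + *h* = 4 + *h*
- longest course: 1 + 3 × 3 + *h* = 10 + *h*

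| Held gap *h* | Calendar days | Duration category in 6.4.3 |
|---|---|---|
| 7 | 11 to 17 | per protocol or acceptable variation |
| 11 | 15 to 21 | per protocol or acceptable variation |
| 12 | 16 to 22 | acceptable, or unacceptable if the other gaps are all 72 h |
| 17 | 21 to 27 | acceptable only if the other gaps are all 24 h |
| 18 | 22 to 28 | unacceptable in every case |

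The 22-day threshold therefore becomes reachable at *h* = 12 (10 + 12 = 22) and certain at *h* = 18 (4 + 18 = 22).

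**Step 5. Sensitivity.** The table does not say when the week starts. If it runs from the day the next fraction was due, the gap is 7 + 1 = 8 to 7 + 3 = 10 days. The course then takes 4 + 8 = 12 to 10 + 10 = 20 days, still below 22. Two separate gaps of exactly 7 days give 1 + 14 + 2 × 1 = 17 to 1 + 14 + 2 × 3 = 21 days.

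**Step 6. Open-ended holds.** Holds until recovery have no fixed length. They may or may not pass 72 hours, 15 days or 21 days; the document gives no recovery times from which to say how often.

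**The case against.** The strongest reply on the grade 4 rows is that 6.4.6 follows directly after 6.4.5 and reads as the specific rule behind a general sentence. That sentence makes resumption only possible, requires the physician's recommendation, and is followed by one that foresees early stopping. This is a reasonable reading, but the site has to supply it: no text gives the table precedence. It narrows the conflict without removing it.

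On timing, the reply is that the fraction interval is worded as what should happen, that a modification table exists to depart from the planned schedule, and that the 16 to 21 day band already leaves room for interruptions. Much of this stands. The bands are compliance scores and carry no stated penalty. Section 8.1 defines the study population as patients who complete TACE, so a duration label removes nobody from the primary or secondary analyses. What remains is that neither the interval nor the 22-day category says how a mandated hold is treated.

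Three stronger readings are tempting and should not be adopted:

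- *The schedule contradicts itself, because gaps of at most 72 hours end by day 13 yet 15 days are allowed.* An outer limit wider than the tightest arithmetic is slack, not a contradiction. The 13-day figure also assumes that all targets share the same fraction days, which 6.4.3 does not state.
- *The two sections set different restart grades.* Resolution in 6.4.5 can mean simply that the grade 3 or 4 trigger has gone, which matches grade 2 or lower in 6.4.6.
- *About 2 to 5 of 33 patients are affected.* That comes from assuming a 5 to 15% hold rate (0.05 × 33 = 1.65; 0.15 × 33 = 4.95). The rate is not in the document, and it describes any hold, not the two disputed grade 4 rows or holds long enough to reach day 22.

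**Conclusion.** The point holds in two parts of unequal weight.

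The main part is the conflict over grade 4 gastrointestinal and grade 4 other non-haematological toxicity: two adjoining subsections give different instructions and no precedence is stated. It is limited to those two rows, and it rests on the wording alone.

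The lesser part is the missing link between the holds and the schedule. The one-week holds necessarily exceed the 72-hour interval. For total duration, a reader might infer that following 6.4.6 always produces an unacceptable deviation. It does not: a seven-day gap gives 11 to 17 days, and no row of the table by itself forces a course of 22 days. The supportable statement is that holds without a maximum, combined with no toxicity exemption, can lead to that category once a held gap reaches 12 to 18 days or more. These figures assume one held gap and the other three within 24 to 72 hours.

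The number of patients affected cannot be derived from the document. Sample size, power, type I error and the analysis population are unaffected. The matter is one of clear and consistent safety instructions, and it should be corrected.

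**What to change.** Reconcile 6.4.5 with 6.4.6 so that each type and grade of toxicity has one instruction. Wherever the two could still be read differently, add a sentence saying which section governs.

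Reconcile 6.4.3 with 6.4.6 by stating how a hold required by the table is scored against the fraction interval and the three duration categories, including the case where a course reaches 22 or more calendar days because of such a hold.

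Which clinical rule applies in each case is for the sponsor to decide. The cost is wording in three subsections, with no new procedures, visits or data and no change to the sample size.
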